10.1.6. OCS Dose-Time Profiles

The dose of OCS taken by individual patients on each day according to the OCS diary will be plotted against study day, to show individual OCS dose-time profiles. Similarly, the average OCS dose across subjects for each day per dose group will be plotted against study day. The change from baseline OCS across subjects for each day per dose group will also be plotted against study day. These profile plots will be presented separately for each dose cohort.

One set of plots will have standard errors associated, while another without.

10.1.7. OCS Burden by Baseline characteristics

Each time adjusted AUC for Day 1/51 through end of treatment periods will be summarized using density and box plots against baseline characteristics by treatment. The following baseline parameter and categories will be used.

1. Density and box plots overall, not by treatment.
2. Baseline dyspnea as summarized by BDI total score, in categories of 5 or less and 6 or more.
3. Baseline dyspnea as summarized MRC grade 1 vs. grade 2 or higher.
4. Baseline OCS level (10mg/day vs. >10mg/day),
5. Baseline FEV1 PP 80% or higher vs. below 80%.
6. Baseline FVC PP 80% or higher vs. below 80%.
7. Baseline DLco PP 80% or higher vs. below 80%.
8. Disease duration (\geq median duration vs. $<$ median duration).
9. Sex
10. Race of African American vs. Non-African American (not including missing).

10.2. Immunogenicity

ADA and anti-Jo 1 analyses will use the mITT Set

10.2.1. Incidence and Titer of Positive ADA (anti-ATYR1923).

The number and percentage of patients with ADA titers at any visit (by maximum individual ADA titer), will be summarized, and all ADA data will be listed.

Analysis of ADA results according to published definitions (Shankar et al, 2014) will include

ADA Prevalence: The proportion of all individuals having drug reactive antibodies at any point in time (ATYR1923 and placebo subjects).

Baseline ADA Incidence: The proportion of pre-dose ADA-positive subjects as a percentage of total number of subjects (ATYR1923 and placebo subjects).

Treatment-induced ADA Incidence: The proportion of individuals with ADA any time after ATYR1923 treatment that were ADA negative at baseline.

Treatment-boosted ADA incidence: The proportion of individuals that were ADA positive at baseline who had significant increases in ADA after ATYR1923 treatment. ADA may be analyzed by subgroup.

If warranted, kinetic analyses of ADA over time may be performed.

10.2.2. Incidence and Titer of Positive anti-Jo 1 Ab

The number and percentage of patients with negative (≤ 7 U/mL), equivocal (7-10 U/mL), or positive (>10 U/mL) maximum anti-Jo 1 Ab levels over all scheduled sampling visit will be summarized by treatment group. All anti-Jo 1 Ab data will be listed.

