Table 1: Schedule of Assessments

Study Period							Tr	eatment							
Visit Study Day	Screen -28 to - 1	1 D1	1a W1/ D8	2 W2/ D15	2a W3/ D22	3 W4/ D29	3a, 3b, 3c W5, 6, 7	4 W8/ D57	4a W10/ D71	5 W12/ D85	5a W14/ D99	6 W16/ D113	6a W18/ D127	7 W20/ D141	EOS WK24/ D169
Visit Window (Days)	-	-	-	±2	±3	±3	±2	±3	±3	±3	±3	±3	±3	±3	±3
Written informed consent	X														
Telephone Contact			X		X		X		X		X		X		
Eligibility check	X	X													
Demographics	X														
Medical history	X														
Height & weight ¹	X	X				X		X		X		X		X	
Modified MRC Dyspnea Scale	X														
Physical examination ²	X									X					X
Vital signs ³	X	X		X		X		X		X		X		X	X
Pulse oximetry ⁴	X	X				X		X		X		X		X	X
12-lead ECG ⁵	X	X ⁵				X		X		X ⁵		X		X ⁵	X
Pulmonary Function Tests ⁶	X	X				X		X		X		X		X	X
DLco ⁷		X								X				X	X
Pregnancy test (females only) ⁸	X (serum)	X						X				X			X (serum)
Serum FSH ⁹	X														
Rheumatoid factor		X													
Jo-1 antibody (serum)	X			X		X		X		X		X		X	X
ADA sampling (serum) for anti- ATYR1923 antibodies ¹⁷	X			X		X		X		X		X		X	X
Safety laboratory testing (hematology, clinical chemistry)	X	X		X		X		X		X		X		X	X
Urinalysis ¹⁰	X	X		X		X		X		X		X		X	X
Coagulation laboratory testing (PT, INR, PTT)	X					X		X		X		X		X	X
Serology (HBsAg, anti-HCV, and anti-HIV 1/2 tests)	X														

Study Period							Tr	eatment							
Visit Study Day	Screen	1 D1	1a W1/ D8	2 W2/ D15	2a W3/ D22	3 W4/ D29	3a, 3b, 3c W5, 6, 7	4 W8/ D57	4a W10/ D71	5 W12/ D85	5a W14/ D99	6 W16/ D113	6a W18/ D127	7 W20/ D141	EOS WK24/ D169
Visit Window (Days)	-	-	-	±2	±3	±3	±2	±3	±3	±3	±3	±3	±3	±3	±3
Serum complement, serum tryptase, and IgE ¹¹		X													
Plasma complement ¹¹		X													
¹⁸ F-FDG-PET/CT (optional) ¹²	X											X			
Skin lesion visual assessments (if applicable) ¹³	X			X		X		X		X		X		X	
Skin lesion biopsy (optional for patients at select sites) ¹⁴	X									X					
AE assessment/Concomitant medications		X	X	X	X	X	X	X	X	X	X	X	X	X	X
Randomization ¹⁵		X													
King's Sarcoidosis Questionnaire		X				X		X		X		X		X	X
Leicester Cough Questionnaire		X				X		X		X		X		X	X
Baseline/Transitional Dyspnea Indices		X				X		X		X		X		X	X
Fatigue Assessment Scale		X				X		X		X		X		X	X
Sarcoidosis Assessment Tool		X				X		X		X		X		X	X
Blood sampling (serum) for ATYR1923 PK ¹⁶		X ¹⁶		X		X		X		X		X		X ¹⁶	X
PBMC collection ¹⁸		X								X					X
Serum biomarkers ¹⁹		X								X				X	X
Infusion site examination ²⁰		X				X		X		X		X		X	

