Study drug administration		X				X		X		X		X		X	
OCS Taper ²¹				X		_								_	

ADA = anti-drug antibodies; AE = adverse event; BMI = body mass index; D = Day; ECG = electrocardiogram; EOI = end of infusion; EOS = End-of-Study; ET = Early Termination; FSH = follicle stimulating hormone; HBsAg = hepatitis B surface antigen; HCV = hepatitis C virus; HIV = human immunodeficiency virus; HRCT = high-resolution computed tomography; INR = international normalized ratio; OCS = Oral Corticosteroid; PBMC = peripheral blood mononuclear cell; PD = pharmacodynamics; PET = positron emission tomography; PK = pharmacokinetics; PT = prothrombin time; PTT = partial thromboplastin time; SOI=start of infusion; W = week(s).

On dosing days, all assessments will be performed pre-dose unless otherwise specified.

- 1. **Height** only at Screening.
- 2. Physical examination. Full physical examinations are to be obtained at Screening, Week 12 and 24, abbreviated symptom-directed physical examination may be completed at other visits if needed.

- 3. **Vital signs** are to be obtained at every visit. On study drug administration days, vital signs are to be measured pre-infusion and at 15 and 30 minutes (±5 minutes) and at 1, 2, and 4 hours (±15 minutes) after the start of infusion (SOI). Vital signs are to be measured before blood sample collection. Vital signs will include blood pressure (systolic and diastolic, recorded after lying supine for 5 min), heart rate, respiratory rate. Temperature is to be obtained at Screening and on dosing days at pre-dose, 60 minutes (±15 minutes) after the SOI, and again at 4 hours (±15 minutes) after the SOI.
- 4. **Pulse oximetry:** continuous pulse oximetry is to be measured on dosing days from 5 minutes pre-dose until EOI, and recorded at the same time points as vital signs. On non-dosing days pulse oximetry is to be obtained with vital sign assessments.
- 5. **12-lead ECG** is to be obtained at Screening, within 1-hour pre-dose on dosing days. At Day 1 and Weeks 12 and 20, an ECG is to be obtained at 4 hours (±30 minutes) after SOI. The ECG is to be obtained after patients have been lying supine for 5 minutes.

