4.1.3. Follow-up

All patients are to attend an End-of-Study (EOS) visit at Week 24, ie, 1 month after the last study drug dose. Note that patients with elevated confirmed positive Jo-1 antibody titers or who have ongoing study drug-related TEAEs at Week 24/EOS will continue to be followed until resolution or determined by the Investigator to be stable (eg, by telephone contact or unscheduled visit).

Assessments during follow-up will be performed as presented in the Schedule of Assessments (Table 1).

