9.9. Management of Potential Infusion Related Reactions, Including Anaphylaxis

ATYR1923 is a biologic and as with all biologics there is a risk for IRRs. These reactions typically occur in close temporal relationship with the infusion. They may be related to cytokine release or immune mediated.

A generalized IRR could be occurring when any symptoms begin during the study drug infusion or during the post-infusion observation period. While these symptoms may be self-limiting, such symptoms may signal the possibility of a severe reaction that could escalate into a life-threatening situation.

66

Should a patient develop an IRR the subsequent management will depend on the nature of the IRR. Where the IRR symptoms are not cardiorespiratory in nature i.e. they comprise cutaneous rash, flushing, burning sensation etc. and are mild to moderate in intensity – the patient may complete the infusion and receive subsequent doses. The patient will need to be observed until all symptoms resolve or for 6 hours after the end of the infusion. Subsequent dosing should continue to occur in a facility where the patient can be monitored closely. The Investigator, in consultation with the Medical Monitor, may opt to adjust the infusion duration and/or administer pre-medication (antihistamines, non-steroidal anti-inflammatories and anti-emetics) if clinically indicated, although this is not mandatory.

If the IRR symptoms constitute a cardiorespiratory risk (hypotension, dyspnea, hypoxia etc.) or any severe AE then all further dosing should be stopped for the patient. If necessary, the patient should be transferred to an acute care facility.

Once the patient is stabilized, additional blood samples are to be collected and procedures performed as outlined below:

• Vital signs, pulse oximetry, infusion site examination, and ECGs are to be performed to gather clinical information as soon as possible after the onset of clinical symptoms of a generalized IRR (for instance, immediately after cessation of the study drug infusion if such a reaction is seen). Vital signs are to be monitored as medically indicated and pulse oximetry is to be monitored continuously for at least 2 hours or until the patient has recovered, whichever is longer. ECGs should be repeated as medically indicated.

Once medical treatment of the IRR has begun, blood samples are to be obtained for assessment of:

- Plasma complement factors (C3a, C4a, C5a, Bb, SC5b-9).

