4.2.2. Secondary Endpoints

- 1) Potential to Decrease Background Oral Corticosteroid Dose
 - Time adjusted Area Under the Curve (AUC) of steroid dose administered over the study periods (Day 1 through the end of dosing interval and Day 51 through the end of dosing interval) by treatment cohort
 - Number of patients who achieve the targeted tapered dose of prednisone 5 mg/day (or equivalent) and maintain it through the end of dosing interval by treatment cohort
 - Exposure response analysis comparing steroid dose area under the curve (AUC) with ATYR1923 PK parameters through Week 24. This endpoint is not analyzed based on this analysis plan. A separate document is prepared for all PK related analyses.
- 2) Immunogenicity of multiple IV doses of ATYR1923 in patients with pulmonary sarcoidosis based on the following endpoints:
 - Incidence and titer of positive ADA (anti-ATYR1923) and anti-Jo-1 Ab.

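### The Jo-1 incidence table uses scheduled visits only, so a result raised only in an infusion-reaction sample is listed but not counted

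*SAP*

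**What the plan says.** The secondary endpoint in SAP 4.2.2 is "Incidence and titer of positive ADA (anti-ATYR1923) and anti-Jo-1 Ab", with no limit to scheduled visits. For Jo-1, SAP 10.2.2 sets three categories (negative at or below 7 U/mL, equivocal from 7 to 10, positive above 10) and assigns each patient by a maximum: "maximum anti-Jo 1 Ab levels over all scheduled sampling visit will be summarized by treatment group". The same section adds: "All anti-Jo 1 Ab data will be listed".

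For ADA, SAP 10.2.1 summarizes patients with titers at any visit and defines prevalence by antibodies at any point in time.

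The schedule of assessments (Protocol Table 1) puts Jo-1 samples at Screening, at Weeks 2, 4, 8, 12, 16 and 20, and at Week 24/EOS. There is none on Day 1. Its notes say: "On dosing days, all assessments will be performed pre-dose unless otherwise specified". Protocol 9.9 adds an event-driven draw: "Once medical treatment of the IRR has begun, blood samples are to be obtained for assessment of" a list that includes Jo-1 and ADA.

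**The concern.** A sample taken because an infusion reaction is being treated is one of the few antibody samples in this study prompted by a suspected immune event. The Jo-1 table leaves it out by rule, while the ADA rule, applied to the same blood draw, lets it in. The SAP gives no reason for the difference, and its summary of changes from the protocol (SAP 3.3) does not mention a restriction on Jo-1.

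The error can run in one direction only, because the maximum over a subset of a patient's samples cannot exceed the maximum over all of them. The endpoint matters because Protocol 2.2 and 4.2 link loss of tolerance to HARS, with Jo-1 antibody, to anti-synthetase syndrome, and Protocol 8.5.6 calls for clinical monitoring of patients who develop the antibody. In cohorts this small, the difference between no case and one case is the main thing the table can show.

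**Working it through.** No figure in the documents bears on this point: there is no power calculation and no assumed rate of Jo-1 positivity or infusion reactions. The check is therefore mainly a comparison of texts.

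1. **Is the reaction sample a scheduled one?** No. It depends on an event and is not in the Jo-1 row of Table 1.

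2. **Does the same-day scheduled sample replace it?** No. Infusions are given on Day 1 and at Weeks 4, 8, 12, 16 and 20. Jo-1 is scheduled on all of these days except Day 1, but before dosing, so that sample precedes any reaction to that infusion. For Day 1, the preceding scheduled sample is the Screening one.

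3. **Does a general rule bring it back in?** No. SAP 7.3.2 carries unscheduled results into shift tables with the nearest scheduled test, using the more abnormal value. The Jo-1 table is not a shift table and has its own explicit rule.

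4. **Would a later scheduled sample catch the same antibody?** Usually, if the antibody persists. The next scheduled draw after Day 1 is Day 15, 14 days later. After each later infusion it is 28 days away (for example Day 29 to Day 57, or Day 141 to Day 169). Two cases remain:
   - the level has fallen back to a lower category by the next draw;
   - there is no next draw. Protocol 9.9 stops further dosing after some reactions, Protocol 6.4.2 asks for the final assessments only where feasible, and Protocol 6.3.1 allows telephone contact when visits are delayed or missed.

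5. **What happens to a dosed patient with no post-dose scheduled sample?** The mITT Set, used for this table, requires only some study drug. Screening is a scheduled Jo-1 visit, so it can supply the maximum. Such a patient could be tabulated as negative on a pre-treatment value, whatever a reaction sample showed.

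6. **Scale.** Arm sizes from Protocol 7.1.3: 12 × 2/3 = 8 active and 12 × 1/3 = 4 placebo per cohort; three cohorts give 24 and 12. As an illustration, suppose exactly one active patient is positive only in a reaction sample (exact Clopper-Pearson 95% intervals):

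| Group | Scheduled samples only | All samples | Change |
|---|---|---|---|
| One active cohort | 0/8 = 0% (0 to 36.9%) | 1/8 = 12.5% (0.3 to 52.7%) | 12.5 points |
| Pooled active | 0/24 = 0% (0 to 14.2%) | 1/24 = 4.2% (0.1 to 21.1%) | 4.2 points |

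The same event in the pooled placebo arm would be 1/12 = 8.3 points.

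**The case against.** The strongest reply is that very few patients could be affected. Jo-1 is sampled on every infusion day after Day 1, again at Week 2 and at Week 24/EOS, and patients who stop dosing are asked to return for the EOS visit (Protocol 6.4.1). To be missed, a patient must be in a lower category at every scheduled sample and raised only in the reaction sample. In the first-in-human study none of the 25 exposed subjects became Jo-1 positive, and none had a definitive infusion reaction, though one could not be ruled out (Protocol 2.2). The full listing would show any such result, and the study has 36 planned patients and no formal hypothesis testing. All of this stands and limits the point to a small improvement. It does not make the table's rule match the endpoint or the ADA rule.

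A reader might also infer four stronger claims that the documents do not support:

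- **That antibodies first found after Week 24 are lost.** Protocol 4.1.3 says "patients with elevated confirmed positive Jo-1 antibody titers or who have ongoing study drug-related TEAEs at Week 24/EOS will continue to be followed". The Jo-1 group is already confirmed positive at Week 24/EOS, which is a scheduled sample, so these patients are already counted. A later sample could raise a maximum level but would not be a first detection. The text requires no Jo-1 draw in that follow-up, which may be by telephone.
- **That Screening values inflate incidence.** A Screening level above 7 U/mL is an exclusion criterion, so, barring an eligibility deviation, every dosed patient starts in the negative category. The Screening value can only stand in for missing post-dose data, as in step 5.
- **That every infusion reaction triggers a Jo-1 sample.** Protocol 9.9 ties the draw to treatment having begun and places it after the paragraph on cardiorespiratory or severe reactions. Whether it applies to untreated, milder reactions is unclear.
- **That the loss falls mainly on treated patients.** No reaction rate by arm is given.

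**Conclusion.** The point holds in a narrow form. As written, SAP 10.2.2 leaves out of the incidence table a Jo-1 result that is equivocal or positive only in the reaction sample that Protocol 9.9 requires. The rule can undercount but cannot overcount relative to using all samples. The size stated above is the arithmetic of a single patient, not an expected effect. It assumes planned arm sizes and exactly one affected patient; the true number cannot be estimated from the documents and may be zero. Because all results are listed, nothing is hidden. What could be wrong is the headline count for a secondary endpoint.

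**What to change.** In SAP 10.2.2, define Jo-1 incidence and titre by each patient's maximum over all samples taken after the first dose, scheduled or unscheduled, including infusion-reaction samples. Mark in the table or a footnote any category that rests on an unscheduled sample. Report dosed patients with no post-dose Jo-1 sample in a separate row rather than as negative. This would put Jo-1 on the same footing as the ADA rule in SAP 10.2.1.

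The cost is a short wording change and a small edit to one table program; no new data or visits are needed. If treatment codes have already been opened, keep the table as specified, add the all-samples version beside it, and record the addition as a change in the clinical study report.

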10.2.3. Relationship between Immunogenicity and Adverse Events

Post-hoc analyses may be performed to assess the difference in AE profiles among different immunogenicity titer levels.

11. EXPLORATORY ANALYSES

11.1. Clinical and Biomarker Measures

The following measures (continuous) will be summarized in actual values, change and percent change from baseline for each measured visit. If a parameter is missing at baseline, then the patient will not be included in the analysis of change and percent change from baseline for this parameter. If a post-baseline parameter is missing, then the patient will not be included for that visit in both actual values, change and percent change from baseline. The mITT Set will be used for the analyses below. In addition, all PFT and Quality of Life Questionnaire summaries will also be presented in the EE Set.

Additional exploratory analyses of biomarker data may be performed that is beyond the scope of this SAP and the results from such analyses will be described in a separate report and/or publications.

11.1.1. Pulmonary Function Tests (PFT)

Key PFT Endpoints

Due to patient-to-patient variability with observed values of PFT measurements (FEV1, FVC, DLco etc), the Percent Predicted (“PP”) versions of these endpoints will be the key PFT endpoints for summary, statistical analyses and interpretation of lung function in ATYR1923-C-002. Additional key PFT endpoints are listed in Table 2 below.

PFT endpoints that are not classified as Key PFT endpoints will be termed “Supportive PFT endpoints”. Where it is warranted, descriptive summaries and/or plots may be produced for some of the Supportive PFT endpoints. All PFT data will appear in the data listings.

Key PFT Timepoints

For tables and figures, all scheduled visits (Baseline, Weeks 4, 8, 12, 16, 20, 24. except DLco measures at Baseline, Weeks 12, 20 and 24) will be presented, though Baseline, Weeks 4, 16 and 24 are the main timepoints of interest for interpretation of the study.

aTyr Pharma, Inc.
 Study ATYR1923-C-002 Statistical Analysis Plan
 IND#: 133692

FINAL Version 1.0
 2021-08-02

Table 2 PFT Endpoint Classification with Planned Summaries and Statistical Analyses

Endpoint classification	Descriptive Statistics				Endpoint Derivations*			Statistical Modeling	
	Absolute value at each Visit	Change from Baseline at each Visit	% Change from Baseline at each Visit	Line Plot by Treatment	Categorized Change from Baseline at each Visit (+/- 5%)	Categorized Change from Baseline at each Visit (+/-10%)	Worsening	MMRM (on Absolute Value with Baseline as covariate)	RCRM (on Absolute Value with Baseline as covariate)
Key PFT Endpoints									
PP FEV ₁ (%)	x	x	x	x	x	x		x	x
PP FVC (%)	x	x	x	x	x	x	x	x	x
PP FEV ₁ /FVC (%)	x	x	x	x	x	x		x	x
PP DLco (%)	x	x	x	x	x	x		x	x
PP DLco adjusted for HgB (%)	x	x	x	x	x	x		x	x
DLco/VA adjusted for HgB	x	x	x	x	x	x		x	x
Supportive PFT Endpoints									
FEV ₁ (L)	x	x	x	x					
FVC (L)	x	x	x	x					
FEV ₁ /FVC	x	x	x	x					
DLco	x	x	x	x					

aTyr Pharma, Inc.
 Study ATYR1923-C-002 Statistical Analysis Plan
 IND#: 133692

FINAL Version 1.0
 2021-08-02

Endpoint classification	Descriptive Statistics				Endpoint Derivations*			Statistical Modeling	
	Absolute value at each Visit	Change from Baseline at each Visit	% Change from Baseline at each Visit	Line Plot by Treatment	Categorized Change from Baseline at each Visit (+/- 5%)	Categorized Change from Baseline at each Visit (+/-10%)	Worsening	MMRM (on Absolute Value with Baseline as covariate)	RCRM (on Absolute Value with Baseline as covariate)
DLco adjusted for HgB	x	x	x	x					
VA	x	x	x	x					
DLco/VA	x	x	x	x					
PEF (L/min)	x	x	x	x					
IVC	x	x	x	x					

* Endpoint derivations:

Endpoint	Derivation rule	Handling of missing values	Statistical analysis
Categorized changes (+/- 5%, +/-10%)	Decrease >5%, Within +/-5%, Increase >5%. Similarly for 10%. For the first 5 key parameters, change here refers to post-baseline minus baseline in the percent predicted. For the DLco/VA adjusted for HgB, this change refers to post-baseline minus baseline divided by baseline.	Missing values are excluded from the “n” count in the summary table	Frequency tables by-visit. Mean PFT value by treatment is plotted against study day. No statistical hypothesis testing to be performed.
Worsening	Two consecutive values with decreases of >5% from baseline. The percent change	If there are 1 or more missed visits between 2 values below the 5% cutoff then classify the patient as Worsened. Rationale is that we	statistical analytical modeling will be performed as detailed in Sections 11.1.1.1 and 11.1.1.2.

aTyr Pharma, Inc.
Study ATYR1923-C-002 Statistical Analysis Plan
IND#: 133692

FINAL Version 1.0
2021-08-02

	here is calculated similarly as the row above.	implicitly assume that the patient has stayed below the cutoff during those missing visits	
--	--	--	--

